2.4.3 Primary analysis

The primary efficacy endpoint will be the composite responder rate based on the LCL-ILA and LCL-SLA of lateral canthal line severity at maximum smile at Month 1 (described in Section 1.3.1 and Section 1.3.2, respectively). To evaluate the effectiveness of QM1114-DP versus placebo in the treatment of moderate to severe LCL, the responder rates of the QM1114-DP and placebo will be compared using the Cochran-Mantel-Haenszel (CMH) test, stratified by site, at the 5% significance level (2-sided).

The null hypothesis of no relationship between treatment and responder rate (i.e. the responder rates are the same in both groups) will be tested against the alternative hypothesis that there is a relationship between treatment and responder rate (i.e. the responder rates are different in the two groups). For a significant result, the two-sided p-value of the comparison of the composite LCL-ILA/LCL-SLA responder rates between the QM1114-DP treated and placebo treated subjects at

Doc id 43QM1901 Statistical Analysis Plan US - QM1114-DP - LCL 👶 GALDERMA MA-43263

Print date:

2021-04-15 15:20

Month 1 using the CMH test needs to be smaller than 0.05. The Breslow-Day test will be used to assess the homogeneity of the odds ratios across all sites.

The estimates of the composite LCL-ILA/LCL-SLA responder rates in each treatment group will be presented as well as the difference in responder rates (QM1114-DP responder rate – placebo responder rate). Corresponding 95% CI for the treatment group composite LCL-ILA/LCL-SLA responder rates and the difference in responder rates along with the p-value for the difference will also be presented. The normal approximation (Wald) method will be used to calculate both the 95% CI for the individual treatment group composite LCL-ILA/LCL-SLA responder rates and the 95% CI for the difference in responder rates. The above responder rates will be presented in figures by visit and treatment group.

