43QM1901 Clinical Study Protocol - QM1114 - LCL

Doc id

Print date:

MA-40370

12.1 I	Protocol Version 3.0 to Version 4.0	
13. LIT	TERATURE REFERENCE LIST74	
14. API	PENDICES75	
Appendix	1 Validated Investigator 4-point Photographic Scale of Lateral Canthal Line Severity (LCL-ILA)	
Appendix S	2 Validated Subject 4-point Photographic Scale of Lateral Canthal Line Severity (LCL-SLA)	
CCI		
Appendix	6 Focused Physical Examination Form Example	
Appendix	7 Adverse Events Potentially Suggestive of Remote Spread of Toxin86	
SIGNED	SIGNED AGREEMENT OF THE CLINICAL STUDY PROTOCOL87	
	List of Tables	
Table 1	Clinical Study Schematic	
Table 2	Schedule of Assessments	
Table 3	Description and Usage of the Study Products	
	List of Figures	
Figure 1	Study Flow Chart	
Figure 2	Injection Sites for Treating LCL Option 1	
Figure 3	Injection Sites for Treating LCL Option 2	

43QM1901 Clinical Study Protocol - QM1114 - LCL ♣ GALDERMA

Doc id

Print date:

MA-40370

SYNOPSIS		
Clinical Study Title: A Multicenter, Randomized, Double-Blind, Placebo-Controlled Study to Evaluate the Efficacy and Safety of QM1114-DP for the Treatment of Moderate to Severe Lateral Canthal Lines (READY – 2)		
Short Title: QM1114-DP Lateral Canthal Lines		
Clinical Study Population:	Male and female subjects, 18 years of age and older, with moderate to severe lateral canthal lines (LCL) at maximum smile.	
Clinical Study Design:	This is a phase 3, multi-center, randomized, double blind, placebo- controlled study to evaluate the efficacy and safety of 60 units (U) of QM1114-DP for the treatment of moderate to severe LCL.	
	Following the informed consent and the screening process, eligible subjects will be randomly assigned in a 3:1 ratio to receive a single treatment at baseline of 60 units QM1114-DP (225 subjects) or placebo (75 subjects) in the LCL areas. Randomization will be stratified by study center.	
	Each subject will receive a single treatment divided equally among 6 injection points (0.1 mL per injection point) in the LCL region.	
	Following treatment at baseline, subjects will be monitored for safety and efficacy for 6 months.	
Target Indication:	This study is designed to evaluate the safety and efficacy of QM1114-DP for the treatment of moderate to severe LCL.	
Total Number of Subjects (Planned):	Approximately 300 subjects will be enrolled.	
Number of Clinical Study Centers (Planned):	Up to 15 centers	
Region(s) / Country(ies) Involved (Planned):	US and Canada	

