1.3 Risk/Benefit Assessment

Based on the clinical experience with QM1114-DP in the Phase 1 study participating in the study may experience AEs such as administrative site conditions (e.g., injection site erythema or sensation of pressure) or headache (Section 1.2.3). 12

occurring may be reduced by using physicians who are experienced in the botulinum toxin injection technique. All treating Investigators will be trained in the administration technique of QM-1114-DP prior to the study start.

The benefit to subjects receiving QM1114-DP in this study will be a temporary reduction in the appearance of their LCL. The subjects in the placebo group are not expected to gain any clinical benefit from their participation in the study; however, as this is an aesthetic indication there are no sequelae to lack of efficacy beyond a disappointment in the reduction of severity of their LCL. In addition, only one subject out of four will receive placebo in the study.

No additional risks specific to the QM1114-DP 60 U dose are anticipated, and sufficient clinical experience with BoNT-A products with similar mode of action for facial aesthetic use at dose levels corresponding to the dose levels in this study demonstrate the potential benefit of the proposed treatments. Adverse events will be recorded at each study visit, and subjects will also be queried for any potential signs and symptoms of local and distant spread of the toxin effect.

In conclusion, given the anticipated low level of transient and acceptable risks, the risk/benefit assessment of the use of QM1114-DP for the treatment of moderate to severe LCL appears to offer a substantial clinical benefit at reasonable risk.

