5. SELECTION AND DISPOSITION OF CLINICAL STUDY POPULATION

5.1 Number of Subjects

As a screen failure rate of approximately 10 percent is anticipated, approximately 330 subjects will be screened in order to get 300 subjects enrolled in a 3:1 ratio to QM1114-DP 60 U (N=225) or placebo (N=75). It is expected that each center will recruit a similar number of subjects.

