2.1 General methods

All tables, listings, and figures will be programmed using SAS Version 9.4 or higher. Data collected in this study will be documented using summary tables and subject data listings created by using the SAS® system. Confidence intervals (CI) and p-values will be 2-sided and performed at a significance level of 5%, unless otherwise specified. Data for all subjects in the clinical database will be included in the data listings. Calculated (derived) variables will be listed as appropriate. Any changes from the SAP will be detailed in the clinical study report.

All efficacy, safety and baseline characteristics variables will be presented using descriptive statistics within each treatment group, and graphs as appropriate. Continuous variables will be summarized using descriptive statistics (number of observations, mean, standard deviation [SD], median, minimum, and maximum). Categorical variables will be presented in frequency tables with number and percentage of observations for each level. Missing counts for all variables will be presented for informational purposes only and will not be included in percentage calculations.

Study days will be calculated relative to the injection of study drug. Day 0 will be the day of study drug administration. Baseline will be the last assessment prior to the injection of study drug unless otherwise indicated. The Screening Visit 1 (Day -14 to Day 0) will be considered the visit prior to injection of study drug. Because the Screening visit and Baseline visit (Day 0) may be performed on the same day, the Screening visit can also be Day 0.

Adverse events, cosmetic/aesthetic procedures and implant history events, medical history events, and concomitant treatments/procedures will be coded using MedDRA, Version 23.0. Prior/concomitant medications and procedural anesthetics will be coded using the World Health Organization (WHO) Drug Dictionary Global, 1 Sep 2019 B3 or higher.

In general, efficacy, safety, col analyses will be performed and summarized by treatment group (QM114-DP, placebo), unless otherwise stated.

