2.4.3.2 Subgroup analysis

Additionally, to evaluate the consistency of the results of the primary analysis across different subgroups of interest, the primary analysis specified above (Section 2.4.3) will be repeated, stratifying for each of the following subgroups specified below:

- Age (less than 65 years old, 65+ years old)
- Gender (Male, Female; if enough males are recruited)
- Baseline Severity score of the LCL-ILA at maximum smile (Grade 2 (Moderate), Grade 3 (Severe), using the worst value from the right and left sides).
- Prior botulinum toxin use (Yes, No)
- Fitzpatrick skin type (I-III, IV-VI)
- Site
- Type of Month 1 visit (Onsite, Remote)

For each subgroup, the responder rates, difference in responder rates between the treatment groups, and the corresponding 95% CI will be presented. The Breslow-Day test will be used to assess the homogeneity of the odds ratios across all the subjects within each subgroup. The subgroup analysis for type of Month 1 visit will be performed based on the ITT population.

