2.7.3 Sample size calculation

The study is planned to include approximately 300 subjects, of whom 225 will be treated with QM1114-DP and 75 subjects will receive placebo.

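### Wald intervals and the Breslow-Day test have no sparse-data alternative, so the placebo and site-level results would be unreliable if few placebo subjects respond

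*SAP*

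**What the plan says.** On the composite endpoint, SAP 2.4.3 says: "The normal approximation (Wald) method will be used to calculate both the 95% CI for the individual treatment group composite LCL-ILA/LCL-SLA responder rates". The same sentence extends the method to the difference between arms. For consistency across centres: "The Breslow-Day test will be used to assess the homogeneity of the odds ratios across all sites".

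SAP 2.4.3.2 repeats the primary analysis by age, gender, baseline severity, prior toxin use, skin type, site and type of Month 1 visit. It asks for rates, differences and 95% intervals in each, and adds: "The Breslow-Day test will be used to assess the homogeneity of the odds ratios across all the subjects within each subgroup".

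Neither document gives an exact or score interval, a rule for zero cells, or a step to take when the homogeneity test cannot be formed. Site pooling (SAP 2.1.2) is triggered only when a site enrols fewer than 5 subjects. It does not depend on responder counts.

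The visible text gives no expected placebo responder rate. Two passages bear on it. SAP 1.4.1 requires a score of 0 or 1 and a gain of at least two grades, on both scales and on both sides at the same visit. Protocol 1.3 says: "The subjects in the placebo group are not expected to gain any clinical benefit".

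**The concern.** Entry requires grade 2 or 3 on both scales (Protocol 5.2.1), so a subject who starts at grade 2 must reach grade 0 on that scale to count as a responder. Four such conditions must hold together: two scales, two sides. A low placebo count is therefore plausible.

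The Wald interval takes its width from the observed proportion. At zero responders the width is zero, and at very small counts it is too narrow and extends below 0%. Breslow-Day needs a finite common odds ratio, which does not exist if no placebo subject responds.

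At stake are the printed placebo-arm interval, the intervals at sites and in small subgroups, and the homogeneity check that supports the primary result. Choosing substitutes after unblinding would be post hoc.

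**Working it through.** **Inputs.** SAP 2.7.3 plans about 300 subjects, "of whom 225 will be treated with QM1114-DP and 75 subjects will receive placebo"; a 3:1 split of 300 gives 225 and 75, which agrees. The Protocol synopsis allows "Up to 15 centers", and Protocol 5.1 adds: "It is expected that each center will recruit a similar number of subjects". At 15 centres that is 300/15 = 20 per site, about 15 active and 5 placebo. Responder rates are assumptions, because the documents show none: placebo 0.5–10%, active 20–60%.

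**Placebo interval, whole arm (n = 75).** The Wald limits are p̂ ± 1.96·√(p̂(1 − p̂)/75).

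- 0/75: Wald 0–0%. The Wilson upper limit is 1.96²/(75 + 1.96²) = 3.84/78.84 = 4.9%.
- 1/75: Wald −1.3% to 3.9%; Wilson 0.2–7.2%.
- 3/75: Wald −0.4% to 8.4%; Wilson 1.4–11.1%.

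Exact coverage is the sum of binomial probabilities over the counts whose interval contains the true rate. At a true rate of 1% those counts are 1 to 4, so coverage is 0.3565 + 0.1332 + 0.0327 + 0.0060 = 0.528. P(0/75) is (1 − p)^75.

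| True placebo rate | P(0/75) | Wald coverage | Wilson coverage |
|---|---|---|---|
| 0.5% | 69% | 31% | 95% |
| 1% | 47% | 53% | 96% |
| 2% | 22% | 78% | 94% |
| 3% | 10% | 90% | 97% |
| 5% | 2% | 89% | 95% |
| 8% | 0.2% | 94% | 95% |
| 10% | 0.04% | 94% | 95% |

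Coverage varies between the listed rates. Just below 0.73%, for example, the Wilson interval for 2/75 misses the true rate and coverage is P(X ≤ 1), about 90%. Clopper-Pearson does not fall below 95%.

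**Placebo interval at a site (n = 5).** Zero width occurs with probability (1 − p)^5: 0.99^5 = 95% at a 1% rate, 0.95^5 = 77% at 5% and 0.90^5 = 59% at 10%. For 0/5 the Wilson upper limit is 3.84/8.84 = 43%.

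**Difference interval.** Exact coverage sums the product of the two binomial probabilities over all pairs of counts whose interval contains the true difference. The grid is active 20, 30, 40, 50, 60% by placebo 0.5, 1, 2, 5, 10%.

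| Active vs placebo n | Wald | Newcombe |
|---|---|---|
| 15 vs 5 | 82–95% | 93–99.6% |
| 60 vs 20 | 93–95% | 95–98% |
| 225 vs 75 | 94–95% | 95–97% |

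**Breslow-Day.** The Mantel-Haenszel odds ratio is Σ(aᵢdᵢ/Nᵢ) / Σ(bᵢcᵢ/Nᵢ), where cᵢ is the placebo responder count in stratum i. If every cᵢ is 0 the denominator is 0, the odds ratio is infinite and the test is undefined. The chance is P(0/75): 47% at 1%, 22% at 2%, 2% at 5%. Regional pooling does not change this, because a total of zero is zero in every region. In simulations under a common odds ratio (15 sites, 10 sites or 4 regions; active 30% or 50%; placebo 1–10%), the size of the test when computable was 0.4–4.6% against a nominal 5%. It was conservative in most cases, so a non-significant result is weak evidence of consistency.

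**The case against.** The strongest reply is that the premise is an assumption. No placebo rate is visible, and the sentence in Protocol 1.3 concerns clinical benefit; it is not a responder forecast. A reader might infer that the placebo count is certain to be near zero, but the documents do not support that. At a 5% rate the chance of 3 or fewer among 75 is only 48%, and at 8–10% the whole-arm Wald interval is adequate and Breslow-Day is almost always computable. This stands, and the point is conditional for that reason.

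Second, no decision depends on these outputs. Success rests on the site-stratified CMH p-value, and the secondary sequence also uses CMH. A reader might infer that the primary conclusion or the main effect estimate is at risk. Neither is: the full-sample difference interval covers 94–95%.

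Third, not every subgroup interval is affected. With 60 versus 20 or more, Wald difference coverage is 93–95%; the problem is at sites and in small subgroups.

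Fourth, the figures describe complete data. The primary analysis pools five imputed datasets in the mITT population, which excludes subjects with a remote Month 1 assessment. Imputation might add placebo responders. But if all five datasets have none, the placebo variance passed to the pooling step is still zero, and the planned BOCF repeat makes a missing score a non-response.

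Finally, one could object that the test is stratified by site while the interval is specified without stratification. A crude difference beside a CMH p-value answers a legitimate question, and no harm has been shown, so this is a preference and not part of the point.

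**Conclusion.** The point holds conditionally, as a reporting weakness that should be corrected. If the true placebo rate is 0.5–5%, the specified whole-arm placebo interval covers 31–90% at the rates tabulated, against a nominal 95%, and prints impossible or zero-width limits at 0–3 responders. At sites with about 5 placebo subjects, a zero-width placebo interval is more likely than not even at a 10% rate, and coverage of the site difference interval can fall to 82%. Breslow-Day may be undefined, mainly at placebo rates of about 2% or lower.

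This rests on the assumed rates, 15 equal sites, 75 placebo subjects and no missing data. If regional pooling is triggered, strata hold about 19 placebo subjects (75/4), and the chance of a zero-width placebo interval drops to 0.95^19 = 38% at a 5% rate and 0.90^19 = 14% at 10%.

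**What to change.** In SAP 2.4.3 and 2.4.3.2, before unblinding:

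- Use Wilson or Clopper-Pearson limits for single-arm responder rates.
- Use Newcombe or Miettinen-Nurminen limits for differences at sites and in small subgroups. The Wald difference interval can stay for the full sample.
- State how these limits are obtained under multiple imputation, since score and exact limits are not an estimate with a standard error and do not pass directly through MIANALYZE. One option is Wilson limits adapted for multiple imputation in the pooled analysis, with direct score limits in the BOCF and observed-case analyses.
- State that Breslow-Day is supportive only. If it cannot be computed because no placebo subject responds, report site and subgroup risk differences with score intervals in a forest plot. Zelen's exact test is no substitute in that case: with no placebo responders only one table configuration is possible, so its p-value is 1.

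The cost is SAP wording, some extra programming for the imputed data, and wider placebo and small-subgroup intervals (0/75 goes from 0–0% to 0–4.9%, and 0/5 from 0–0% to 0–43%).

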2.4.3.1 Sensitivity analysis

To evaluate the impact of missing data on the primary endpoint, sensitivity analyses will be performed. The primary analysis specified in Section 2.4.3 will be repeated using the BOCF method (detailed in Section 2.4.2), and also using the ITT OC.

In addition, a sensitivity analysis of the primary efficacy endpoint will be performed based on the PP population, and also on the Safety population to account for potential errors in randomization. The analysis method described above in Section 2.4.3 will be repeated but using the PP population and Safety population.

2.4.3.2 Subgroup analysis

Additionally, to evaluate the consistency of the results of the primary analysis across different subgroups of interest, the primary analysis specified above (Section 2.4.3) will be repeated, stratifying for each of the following subgroups specified below:

- Age (less than 65 years old, 65+ years old)
- Gender (Male, Female; if enough males are recruited)
- Baseline Severity score of the LCL-ILA at maximum smile (Grade 2 (Moderate), Grade 3 (Severe), using the worst value from the right and left sides).
- Prior botulinum toxin use (Yes, No)
- Fitzpatrick skin type (I-III, IV-VI)
- Site
- Type of Month 1 visit (Onsite, Remote)

For each subgroup, the responder rates, difference in responder rates between the treatment groups, and the corresponding 95% CI will be presented. The Breslow-Day test will be used to assess the homogeneity of the odds ratios across all the subjects within each subgroup. The subgroup analysis for type of Month 1 visit will be performed based on the ITT population.

2.4.4 Secondary analysis

To evaluate the effectiveness of QM1114-DP versus placebo in the treatment of moderate to severe LCL, the proportion of subjects who achieve 0 or 1 on the LCL-ILA at maximum smile at Month 1 and at all the rest of the post-treatment visits will be compared using the CMH test, stratified by site. To control the type I error rate, the fixed sequence testing procedure will be used, which requires no adjustment to the level of significance. However, the comparisons must be made in a pre-specified order following the procedure outlined below:

Print date:

2021-04-15 15:20

1. Primary analysis must be done first, prior to any other analysis

Secondary analyses:

- 2. Month 1 responder rate
- 3. Day 14 responder rate
- Month 2 responder rate
- Month 3 responder rate
- Month 4 responder rate
- Month 5 responder rate
- Month 6 responder rate
- Day 7 responder rate

If one of the tests in the sequence is not significant (p > 0.05), no confirmatory claims can be made based on tests following (and including) that one.

The secondary analysis in the sequence will be based on the ITT population with the remote visit assessments excluded. A sensitivity analysis will be conducted using the ITT population including the remote visit assessments.

[figure not shown]
Results will include estimates of the percentages, difference in percentages, 95% CIs, and CMH pvalue as well as a graph showing the percentages for the two treatment groups over time. For consistency across strata, the Breslow-Day test will be used.

Doc id 43QM1901 Statistical Analysis Plan US - QM1114-DP - LCL 🖧 GALDERMA MA-43263

Print date:

2021-04-15 15:20

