5.2.1 Inclusion Criteria

- Male or female 18 years of age or older.
- 2. Moderate to severe bilaterally symmetrical LCL (grade 2 or 3 on the 4-point Photographic Scale ranging from 0 [none] to 3 [severe]) at maximum smile as assessed by the Investigator live assessment (LCL-ILA).
- 3. Bilaterally symmetrical LCL graded as Level 2 or Level 3 on the 4-point Photographic Scale (ranging from Level 0 to Level 3) at maximum smile as assessed by the subject live assessment (LCL-SLA).
- 4. Female of non-childbearing potential (i.e., post-menopausal [absence of menstrual bleeding for 1 year prior to screening, without any other medical reason], or has undergone hysterectomy or bilateral oophorectomy).

OR

Female of childbearing potential with a negative urine pregnancy test at screening and baseline, and agrees to use a highly effective and approved contraceptive method for the duration of the study. A highly effective method of contraception is defined as:

- Bilateral tubal ligation;
- Combined (estrogen and progesterone containing) oral, intravaginal or transdermal contraceptives that inhibit ovulation as the primary mode of action, on a stable dose for at least 28 days prior to screening visit;
- Intra uterine device (IUD) inserted at least 28 days prior to screening visit;
- Intrauterine hormone-releasing system;
- Partner vasectomized for at least three months prior to screening visit;
- Progestogen-only oral, injectable or implantable contraceptives that inhibit ovulation as the primary mode of action, on a stable dose for at least 28 days prior to screening visit;
- Strict abstinence (i.e., refraining from heterosexual intercourse for the entire duration of the subject's participation in the study).
- 5. Time and ability to complete the study and comply with instructions.
- Understands the study requirements and signed the informed consent form (ICF).

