9.1.5 Inferential Statistical Analyses

The primary efficacy endpoint will be a composite responder rate based on the LCL-ILA and LCL-SLA assessments of lateral canthal line severity at maximum smile at Month 1. Responder is defined as a subject who achieves grade/level 0 or 1 and at least 2 grades improvement from baseline, on both scales concurrently. The null hypothesis of no relationship between treatment and responder rate will be tested against the alternative hypothesis that there is a relationship between treatment and responder rate. The responder rates of the QM1114-DP and placebo will thus be compared using Cochran-Mantel-Haenszel test, stratified by center, 5% significance (2-sided). Depending on the number of centers, pooling of centers might be needed. For the primary efficacy endpoint, consistency of the results will be analyzed using Cochran-Mantel-Haenszel test stratified by gender, baseline ILA, prior use of botulinum toxin, and Fitzpatrick skin type, respectively.

The analysis of the primary efficacy endpoint will be based on the mITT population. A sensitivity analysis of the primary efficacy endpoint will be performed using the ITT population.

Print date:

2020-06-11 13:03

For the secondary endpoints, the Cochran-Mantel-Haenszel test will be used to compare the proportion of subjects who achieve 0 or 1 on the LCL-ILA at maximum frown at Month 1 and at all the rest of the post-treatment visits. To control the type I error rate, the fixed sequence testing procedure will be used, which requires no adjustment to the level of significance. However the comparisons must be made in a pre-specified order following the procedure outlined below:

Primary analysis

Secondary analysis:

- Month 1
- Day 14
- Month 2
- Month 3
- Month 4
- Month 5
- Month 6
- Day 7

If one of the tests in the sequence is not significant (p > 0.05), no confirmatory claims can be made based on tests following (and including) that one.

The secondary analysis in the sequence will be based on the ITT population with the remote visit assessments excluded. A sensitivity analysis will be run using the ITT population including the remote visit assessments.

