1.4.2 Secondary efficacy endpoints

Secondary endpoints include:

(i) Percentage of subjects who achieve a score of 0 or 1 at the same visit for both left and right sides summarized for each post-treatment visit using the LCL-ILA at maximum smile

Doc id

Effective

Version: 1.0

Title 43QM1901 Statistical Analysis Plan US - QM1114-DP - LCL

MA-43263

Effective date: 2021-02-05 13:17

43QM1901 Statistical Analysis Plan US - QM1114-DP - LCL

MA-43263

Doc id

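### The confirmatory secondary CMH tests are valid, but adding baseline LCL-ILA grade to coarsely pooled site strata would probably make the late-visit tests somewhat more efficient

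*SAP*

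**What the plan says.** SAP 2.4.4 compares the proportion at LCL-ILA 0 or 1 at Month 1 "and at all the rest of the post-treatment visits will be compared using the CMH test, stratified by site". The protocol synopsis likewise stratifies the secondary CMH tests by center, and randomization is stratified by center only. The endpoint in SAP 1.4.2 is "Percentage of subjects who achieve a score of 0 or 1 at the same visit for both left and right sides". The tests run in a fixed order after the primary: Month 1, Day 14, Months 2 to 6, then Day 7. The stopping rule reads "If one of the tests in the sequence is not significant (p > 0.05), no confirmatory claims can be made" from that test onward.

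Entry requires LCL-ILA grade 2 or 3 at maximum smile (Protocol 5.2.1). Baseline grade is used in two places, both for the Month 1 primary endpoint. Protocol 9.1.5 plans a consistency CMH "stratified by gender, baseline ILA, prior use of botulinum toxin" and Fitzpatrick skin type, taken one at a time. SAP 2.4.3.2 lists "Baseline Severity score of the LCL-ILA at maximum smile" as a subgroup factor, coded grade 2 vs 3 from the worse side. Neither document says why grade is absent from the eight secondary tests.

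SAP 2.1.2 pools sites into geographic regions only if some site enrolls fewer than 5 subjects.

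**The concern.** A subject entering at grade 2 reaches 0 or 1 with one grade of improvement; a subject entering at grade 3 needs two. Baseline grade is therefore part of how hard the endpoint is to reach, and is plausibly a strong predictor of response in both arms. Stratifying a CMH test on a strong predictor removes variation that otherwise dilutes the treatment comparison.

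The late visits are where this could matter. Protocol 1.1 puts the usual duration of effect for the drug class at about 4–6 months, so responder rates may be falling at Months 4 to 6. About 75 placebo subjects are planned. The secondary tests use observed cases (SAP 2.4.2) with remote assessments excluded, so the number analyzed can only be smaller than 300. One non-significant visit ends confirmatory claims for that visit and all after it.

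**Working it through.** **Inputs from the documents.** 225 active and 75 placebo (SAP 2.7.3); 3:1 randomization stratified by site, up to 15 sites (SAP 1.1.2); two-sided 5% level (SAP 2.1). There is no readable power figure for the secondary tests to reproduce, because the sample size rests on exposure and safety data (SAP 2.7).

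**Assumed inputs.** Late-visit responder rates, share of grade 3, and the odds ratio for response, grade 2 vs grade 3, within arm.

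**Stratum sizes.** 300/15 = 20 subjects per site, 5 on placebo. Crossing with grade gives 30 strata averaging 10 subjects and 75/30 = 2.5 on placebo. Four regions by grade gives 8 strata averaging 37.5 subjects and 75/8 = 9.4 on placebo.

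**Cost when grade does not predict response.** The CMH statistic is [Σ(a − n₁m₁/N)]² / Σ[n₁n₀m₁m₀/(N²(N − 1))], where a is active responders, n₁ and n₀ the arm sizes, and m₁ and m₀ responders and non-responders in a stratum of N. Its information is proportional to Σ n₁n₀/N. If a balanced block of N subjects is split by an unrelated two-level factor, the expected information is multiplied by (N − 2)/(N − 1).

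- Site (N = 20): 18/19 = 0.947, a 5.3% loss.
- Region (N = 75): about 73/74 = 0.986, a 1.4% loss.

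At 68.3% power the standardized effect is 1.960 + 0.476 = 2.436. Multiplying by √0.947 gives 2.371 and power Φ(0.411) = 66.0%, a loss of 2.3 points. Multiplying by √0.986 gives 2.420 and power Φ(0.460) = 67.7%, a loss of 0.6 points. The simulation below gives losses of 2.4 and 0.6.

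**Simulation.** 10,000 trials per scenario, 15 sites of 20 (15 active, 5 placebo), common odds ratio within grade, no site effect, no missing data, all stratifications applied to the same simulated data. Power (%) with half the subjects at grade 3, site-only → four regions by grade:

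| Placebo / active | Grade OR 1 | OR 3 | OR 5 | OR 10 |
|---|---|---|---|---|
| 5% / 15% | 68.3 → 67.7 (−0.6) | 67.0 → 67.7 (+0.7) | 67.8 → 70.0 (+2.2) | 67.8 → 71.5 (+3.7) |
| 5% / 20% | 93.1 → 92.9 (−0.2) | 93.4 → 93.8 (+0.4) | 93.9 → 94.6 (+0.7) | 93.6 → 95.3 (+1.7) |
| 10% / 25% | 84.0 → 83.7 (−0.3) | 83.2 → 84.5 (+1.3) | 84.0 → 86.3 (+2.3) | 83.6 → 88.1 (+4.5) |
| 20% / 37% | 80.2 → 79.7 (−0.5) | 80.2 → 82.3 (+2.1) | 79.8 → 84.2 (+4.4) | 80.2 → 87.6 (+7.4) |

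- With 70% at grade 3, the largest gain is 80.0 → 89.0 (+9.0), at 20% / 37% and odds ratio 10.
- At lower rates (2% / 10% and 3% / 12%, half grade 3) the change is −0.7 to −0.8 at odds ratio 1, +0.4 to +0.5 at 3, +0.8 to +1.4 at 5 and +1.9 to +2.7 at 10.
- Crossing grade with all 15 sites, for the four rate pairs in the table, gives −1.7 to −2.4 at odds ratio 1, −1.2 to +0.4 at 3, −0.1 to +2.9 at 5 and +1.0 to +6.5 at 10. Across all rates and grade mixes examined, the worst loss at odds ratio 1 was 2.6 points.
- Type I error was 4.3–5.1% for every stratification.

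**The case against.** The strongest reply is that nothing is wrong with the plan. The site-only CMH matches the randomization strata, agrees with the protocol and holds its level. Omitting one prognostic factor is a legitimate choice. That stands, and it is why this is an efficiency point.

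A reader might go further than the documents allow and infer that the late-visit tests lose power for nothing, and that adding grade is free. Two things count against this. First, thin strata have a cost. If no site falls below 5 subjects, SAP 2.1.2 leaves sites unpooled, and crossing grade with them can lose 2–3 points. Second, a gain of 5–8 points at half grade 3 generally needs a very strong grade effect. For example, assume placebo response of 22% at grade 2 and 1% at grade 3, and active response of 50%/6%, 41%/4% or 35%/3%. Five site pools by grade then raise power from 86% to 92%, 56% to 64% and 29% to 34%. The implied grade odds ratios are (0.22/0.78)/(0.01/0.99) = 28 on placebo and about 16–17 on active. Keeping the same overall rates and weakening only the grade effect cuts the gain to 1.7–3.0 points at an odds ratio of 5 and 0.7–1.1 at 3. Needing two grades rather than one makes grade plausibly prognostic; it does not establish odds ratios of that size.

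Nor does omitting grade put Day 7 at risk. Its exposure comes from being placed last in the sequence.

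The simulation's lack of a site effect favors pooling. In the strong-effect scenarios, adding between-site variation (SD 0.5 on the logit scale) left the gains almost unchanged: 86.1 → 91.6, 55.2 → 63.1 and 29.8 → 34.2.

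**Conclusion.** The point holds as a modest, conditional efficiency gain. For grade odds ratios of 3 to 10 and half the subjects at grade 3, region by grade strata gain between about 0 and 7 points; a larger share at grade 3 extends this to 9. The gain is smallest where rates are very low or power is already above 90%. If grade is unrelated to response, the loss is about 1 point. The balance favors the change because the endpoint's definition makes some grade effect likely, and because power at Months 4 to 6 decides how far confirmatory claims can run.

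Every power figure rests on assumed rates, grade mix and grade effect, with about 20 subjects per site and complete data. The simulation used four regions. SAP 2.1.2 can produce up to eight if Canada has more than one site, giving up to 16 strata; the thin-stratum cost should then lie between the four-region and 15-site results.

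**What to change.** Before unblinding, change SAP 2.4.4 so that each secondary test is a CMH stratified by geographic region and baseline LCL-ILA grade at maximum smile (2 vs 3, worse side, as coded in SAP 2.4.3.2). State that the SAP 2.1.2 regions apply to these tests whether or not any site enrolls fewer than 5 subjects, and that grade is not crossed with unpooled sites. Keep the site-only CMH as a named sensitivity analysis. Leave the order of the sequence and the 5% level unchanged. Record the change in SAP 2.8, because the protocol synopsis specifies stratification by center.

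The cost is SAP wording and minor programming. The variable is already collected and coded, and no extra data or subjects are needed. The statistical price is a loss of about 1 point of power if grade proves not to be prognostic. If unblinding has already happened, the site-only test must remain the confirmatory one and the stratified version can only be supportive.
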